4. SELECTION AND ENROLLMENT OF PARTICIPANTS

4.1 Inclusion Criteria

Subjects must meet all of the inclusion criteria to participate in this study.

1. Adults aged 18 years and above, with mild to severe persistent asthma will be enrolled as defined by The NIH National Asthma Education and Prevention Program (NAEPP) Guidelines for Assessing Asthma Severity¹ (please see table page 9). Subjects will have asthma which is not optimally controlled as defined by Asthma Control Test (ACT) score, despite the current use of inhaled corticosteroids with or without inhaled long-acting beta agonists.
2. Treatment with inhaled corticosteroids (ICS) +/- long acting β -agonists/long acting muscarinics and montelukast;
3. Physician diagnosed asthma, confirmed by patient history/report, as well as pulmonary function test (FEV1 \geq 60% of predicted or 1.5 L) and methacholine testing (Baseline methacholine PD20 < 16 mg/ml if taking ICS or < 8 mg/ml if not taking ICS at Visit 2) to confirm diagnosis.
4. Non-smoker (e.g., tobacco, e-cigarette, marijuana) for \geq 1 yr.; Nicotine patch or gum is allowed.
5. \leq 10 pack-year smoking history;
6. Suboptimal control of asthma as determined by a score < 19 or less on the Asthma Control Test (ACT) at Screening and Randomization Visits.
7. Ability to understand the English or Spanish language and to understand the study procedures and comply with them for the entire study period.
8. Females of childbearing potential: Pregnant or lactating; participants of appropriate age will be screened with urine pregnancy tests at each visit and cannot participate if pregnant. Participants must agree to use effective contraception during the trial.
- 9.

Prior Medical Therapy

Washouts:

The chart below lists medications/substances that decrease airway hyper-responsiveness and should not be taken prior to pulmonary function testing. Withholding times are listed next to the medication.

Medications/Substances	Withhold/Washout Times before test
Caffeine, cola drinks, and chocolate	Avoid the day of
Alcohol	4hrs
Short-acting β -agonists in conventional inhaled doses (e.g. albuterol 200 μ g)	6 hrs
Long-acting β -agonists (e.g. salmeterol)	36 hrs
Ipratropium (Atrovent 40 μ g)	12 hrs
Long-acting anti-muscarinic agents (e.g. tiotropium)	\geq 168 hrs (7days)
Ultra-long-acting β -agonists (i.e. indacaterol, vilanterol, olodaterol) Oral theophylline	24-48 hours (2 days)
Oral theophylline	12-24 Hrs

4.2 Exclusion Criteria

Subjects with any of the exclusion criteria will be excluded from study participation.

1. Other major chronic illnesses: Conditions which in the judgment of the study physician would interfere with participation in the study, e.g., non-skin cancer, uncontrolled diabetes mellitus, coronary artery disease, congestive heart failure, stroke, severe hypertension, renal failure, liver disorders, malabsorption disorders, immunodeficiency states, major neuropsychiatric disorder;
2. Cardiovascular problems:
 - a. Myocardial infarction or stroke in last 3 months
 - b. Uncontrolled hypertension
 - c. Known aortic aneurysm
3. History of physician diagnosis of chronic bronchitis, emphysema or COPD
4. Medication use:
 - a. Current consumption of ginger supplements
 - b. oral corticosteroid use within the past 6 weeks
 - c. use of an investigational treatment in the previous 30 days
 - d. Use of anti-coagulation such as warfarin, rivaroxaban and similar agents.
5. Known adverse reaction to ginger or ginger products
6. Subjects with cancer, other than skin cancer, will be excluded.
7. Current drug or alcohol use or dependence that, in the opinion of the site investigator, would interfere with adherence to study requirements
8. Inability or unwillingness of individual or legal guardian/representative to give written informed consent.

4.3 Study Enrollment Procedures

Participants will be recruited by a variety of methods that have been used previously by the study team. These methods may include solicitation in physician offices, clinics, workplaces, and public media advertisements. All public advertisements will first be approved by the Institutional Review Board (IRB).

Potential enrollees will be approached either in person, by telephone or by mail to establish general eligibility criteria.

Documentation of ineligibility and non-participation of eligible candidates will be recorded within a screening log.

Potential enrollees will meet with the study Coordinator and local physician co-investigators to review the study in a quiet room and will be given as much time as needed to read the consent and ask questions. The consents, HIPAA Authorization and all study questionnaires will be available in English and Spanish. If they agree to participate, they will be asked to sign a consent. A copy of the consent form will be given to each participant, and the signed original will be kept in the participant's research chart. Only participants who are capable of providing their own informed consent will be enrolled.

Randomization is a process that assigns participants/subjects by chance (rather than by choice) into specific groups, typically for clinical research and clinical trials. An independent statistician will generate the randomization codes and allocations. The blinded study coordinator will retrieve the randomization allocation through RedCap. RedCap is an institutionally available automated system for randomization and the statistician will have direct oversight over the process. The blinded study team will not have access to the randomization codes. In this module, randomization model is defined as Drug A and Drug B in a 1:1 ratio. Drug A and Drug B may refer to placebo or active drug, however they are left coded as such to ensure blinding. The module creates a template allocation table, which the user uses to structure the randomization table to be imported. The module also monitors the overall allocation progress and assignment of randomized subjects to ensure equal proportions of active drug and placebo. Only one site

member will be allowed randomization privileges, but the site will confirm, and lock the specific data field to ensure that no data is altered after randomization. There is no stratification, and there are no variable block sizes.

5. STUDY INTERVENTIONS

5.1 Interventions, Administration, and Duration

A 28-day supply of study drug (ginger capsules) or placebo (matching capsules) will be dispensed from the Columbia University Medical Center research pharmacy in a blinded fashion and distributed to the study subjects by the clinical research coordinator in the asthma clinic. Patients will take their first dose of study drug at the study site during the randomization visit and will then be instructed to take 1g twice a day with meals in the outpatient setting. Patients participating in the pharmacokinetic studies will be told to hold their daily dose on subsequent clinic visit dates until timed dosing occurs in the clinic.

Potential Adverse Events: Ginger is widely used as an over-the-counter dietary supplement. The formulation and amount of ginger used in this study (2g per day; Pure Encapsulations®) has been chemically characterized by HPLC and has been administered to patients at the oral amount (2 grams) for 28 days in multiple human studies measuring inflammatory mediators in colonic mucosal biopsies. The incidence of side effects in a 28 day trials of 30 individuals were not significantly different in placebo versus ginger and no adverse events were greater than the NCI Common Toxicity Criteria Grade 1. In a second study of 27 individuals no adverse event greater than NCI Common Toxicity Criteria Grade 1 was reported (no placebo comparison) and the leading complaints were gastrointestinal symptoms of eructation, heartburn or indigestion.¹⁵ In a third study of 20 patients consuming the same formulation in the same amount for the same duration (2g, Pure Formulations, 28 days) no statistically significant increase in adverse events occurred compared to placebo, no toxicities were greater than the NCI Common Toxicity Criteria Grade 1 and included bloating, nausea and heartburn.

There have been small numbers of studies reporting on possible inhibition of platelet aggregation by ginger. Ginger has been shown in an in vitro study to inhibit platelet aggregation with a potency similar to that of aspirin and in another study of human volunteers, to have a synergistic effect with nifedipine in platelet aggregation.⁸⁻¹⁰ A single case report has been published demonstrating epistaxis in a woman who was being treated with Coumadin who subsequently started taking ginger.¹¹ Subjects taking anti-coagulation will be excluded from participation, though subjects taking aspirin alone will be included in the study since there have been no studies or reports of increased bleeding risk with aspirin and ginger combined.

Available Supportive Care: A bronchodilator (albuterol/salbuterol) will be available to be administered if the participant is uncomfortable from the effects of the methacholine challenge test. A physician or nurse practitioner will be available during all methacholine tests.

There is no dose escalation component to this study.

No modification to the study interventions will be employed without prior review and approval of the NCCIH, FDA, IRB and DSMB. The leading expected complaints associated with oral ginger consumption are gastrointestinal symptoms of eructation, heartburn or indigestion. We will utilize the National Cancer Institute Common Toxicity Criteria (CTCAE) Grades 1 through 5 with unique clinical descriptions of severity for each AE based on this general guideline:

Grade 1 Mild; asymptomatic or mild symptoms; clinical or diagnostic observations only; intervention not indicated.

Grade 2 Moderate; minimal, local or noninvasive intervention indicated; limiting age-appropriate instrumental ADL.

Grade 3 Severe or medically significant but not immediately life-threatening; hospitalization or prolongation of hospitalization indicated; disabling; limiting self care ADL.

Grade 4 Life-threatening consequences; urgent intervention indicated.

Grade 5 Death related to AE.

FDA IND approves the administration of this dietary supplement from Pure Encapsulations at a dose of 2g/day for a duration of 56 days. No changes in these parameters are anticipated.

5.2 Handling of Study Interventions

The study drug (~500mg capsules) (ginger extract from Pure Encapsulations) and matching placebo have been provided to our research pharmacy and packaged (120 capsules/bottle) by the manufacturer. Each bottle is labeled 'A' or 'B' and the code is held by the research pharmacy. Study drug is stored at room temperature; temperature logs are maintained by Research Pharmacy. For distribution to study subjects, the clinical research coordinator will obtain the appropriately labeled bottle from the research pharmacy on the day of the study visit and distribute to the subject. Unused study drugs and placebo will be destroyed.

Study intervention accountability records will be the case report source documents that will be stored within the study binder and include (1) inclusion/exclusion documentation; (2) medical history; (3) concomitant medications; (4) adverse events; (5) methacholine challenge data; (6) individual source documents for visits 1-5.

There are no lifestyle/behavioral interventions in this study. Not applicable.

The placebo is in an identically appearing capsule as the study compound. Taste of placebo and ginger is matched as per manufacturer.

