If ACT remains ≤ 19 , subjects will be randomized into 2 treatment groups; oral ginger (1g twice per day: Pure Encapsulations™) or matching placebo (*FDA IND in place*: # [REDACTED]). Ratio of randomization will be 1:1. An independent statistician will generate the randomization codes and allocations. The blinded study coordinator will retrieve the randomization allocation for each subject through RedCap. RedCap is an institutionally available automated system for randomization; the independent statistician will have direct oversight over the process. The blinded study team will not have access to the randomization codes.

At the randomization visit, women of child bearing potential will have a negative pregnancy test confirmed, subjects will be asked to complete an ACT to assess asthma control and a validated asthma quality of life questionnaire (Juniper mini AQLQ). Fractional excretion of nitric oxide (FeNO) will be measured using a Circassia Niox Vero machine with disposable filters. Pre-dose basic spirometry will be performed. 10ml of blood will be collected for measurement of baseline cytokines, biomarkers and blood eosinophil count. Subjects will be given their first dose of study drug and post-dose spirometry will be repeated one hour later.

A total of eight subjects will undergo pharmacokinetic (PK) measurements of the key metabolites of active ginger components. For those patients, an additional 35 ml of blood will be collected over an additional 7 times points (pre-dose, 0.5 hour, 1 hour, 2 hour, 3 hour, 4 hour, and 8 hour). The eight subjects will be selected through voluntary participation. The option will be provided to all subjects who sign the consent. Once there have been 4 subjects in Group A and 4 subjects in Group B selected, there will no longer be any additional subjects accepted to join the PK study.

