Day 43-50/Visit 4: Subjects will be asked to withhold morning dose of the study drug the day of the study visit. Women of child bearing potential will have a negative pregnancy test confirmed. Subjects will be asked to complete an ACT to assess asthma control and a validated asthma quality of life questionnaire (Juniper mini AQLQ). FeNO will be measured using a Circassia Niox Vero machine with disposable filters. Basic spirometry will be performed, Methacholine test will be performed if subject meets safety criteria ($FEV_1 > 1.5L$ or 60% predicted). 10ml of blood will be collected for measurement of cytokines, biomarkers and blood eosinophil count. For those patients in PK group, an additional 35 ml of blood will be collected over an additional 7 times points (pre-dose, 0.5 hour, 1 hour, 2 hour, 3 hour, 4 hour, and 8 hour). Study drug will be administered in the clinic after the pre-dose PK blood draw.

Unused study medication will be collected and pill count will be recorded.

Day 71-78/Visit 5: Subjects will be asked to withhold morning dose of the study drug the day of the study visit. Women of child bearing potential will have a negative pregnancy test confirmed. Subjects will be asked to complete an ACT to assess asthma control and a validated asthma quality of life questionnaire (Juniper mini AQLQ). FeNO will be measured using a Circassia Niox Vero machine with disposable filters. Basic spirometry will be performed. Methacholine hyperresponsiveness will be measured if subject meets safety criteria ($FEV_1 > 1.5L$ or $>60\%$ predicted). 10ml of blood will be collected for measurement of cytokines, biomarkers and blood eosinophil count. For those patients in PK group, an additional 35 ml of blood will be collected over an additional 7 times points (pre-dose, 0.5 hour, 1 hour, 2 hour, 3 hour, 4 hour, and 8 hour). Unused study medication will be collected and pill count will be recorded. Study drug will be administered in the clinic after the pre-dose PK blood draw.

Sample Size and Population

Adults 18 and older, with physician diagnosed mild to severe persistent asthma will be screened. 36 participants will be randomized equally into two arms (18 per group); 1 gram of oral ginger extract twice a day for 28 days or matching placebo. Our sample size analysis requires 16 participant per group and with an anticipated 10% attrition rate, we will enroll 18/group.

Randomization will not be stratified in this pilot study.

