Randomization is a process that assigns participants/subjects by chance (rather than by choice) into specific groups, typically for clinical research and clinical trials. An independent statistician will generate the randomization codes and allocations. The blinded study coordinator will retrieve the randomization allocation through RedCap at the time of the randomization visit. RedCap is an institutionally available automated system for randomization; the independent statistician will have direct oversight over the process. The blinded study team will not have access to the randomization codes. In this module, randomization model is defined as Drug A and Drug B in a 1:1 ratio. Drug A and Drug B may refer to placebo or active drug, however they are left coded as such to ensure blinding. The module creates a template allocation table, which the user uses to structure the randomization table to be imported. The module also monitors the overall allocation progress and assignment of randomized subjects to ensure equal proportions of active drug and placebo. Only one site member will be allowed randomization privileges, but the site will confirm, and lock the specific data field to ensure that no data is altered after randomization. There is no stratification, and there are no variable block sizes.

All evaluations and blood draws will be completed at a single site at a single center, the outpatient clinic of The John Edsall-John Wood Asthma Center at the Columbia University Medical Center. Blood eosinophils will be measured by the Center for Advanced Laboratory Medicine (CALM) with the Department of Pathology and Cell Biology at Columbia University Medical Center. Plasma cytokines will be measured by multiplex array in the laboratory of [name], at Columbia University and the metabolite measurements within the PK studies will be performed by [name], [name].

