6.2.3 Blinding

Ginger extract and placebo capsules have been pre-packaged and labeled with a code by the distributor (Atrium Innovations, Pure Encapsulations) and delivered to the research pharmacy at the Columbia University Medical Center. We do not anticipate any collected data offering evidence of a participant's assignment to a particular arm. All study data is collected objectively without an opportunity for the collected data to identify the study arm. For example, changes in methacholine PD20 and exhaled nitric oxide (primary outcomes) will vary over the course of the study in both ginger and placebo treated subjects. These variations will not be able to offer evidence of group membership and will only be informative after analysis in the aggregate.

The study PIs, [name], [name] are authorized to break the blind if there is a concern for subject safety, a serious adverse event or safety concerns raised by the DSMB. The PIs will contact the independent statistician who will be holding the codes. The PIs, Research Coordinator, study statistician(s), subjects and research pharmacy will be blinded. The research pharmacy will be notified as to randomization to drug A or B but will be unaware of which is ginger versus placebo.

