9.2 Sample Size and Randomization

We utilized published literature to identify the magnitude of change in our primary outcomes that are clinically relevant. As illustrated in the table in section 3, we calculated a need of 14 subjects per arm for the methacholine measurement and 16 subjects per arm for the exhaled nitric oxide assessment (same subjects studied in methacholine and exhaled nitric oxide assays). Thus we need 16 subjects per arm and anticipate a 10% attrition rate overall requiring 36 subjects. As illustrated in the table in section 3, an enhanced tolerance to inhaled methacholine of 0.7X the doubling dose is considered clinically significant.¹² We anticipate a S.D. of 0.6 in both groups and aim to achieve 80% power at the 0.05 significance level. This requires 14 subjects for each of the two arms. For exhaled nitric oxide with baselines starting at >50ppb, a 20% decrease is considered clinically significant. We expect a S.D. of ~ 37 and aim to achieve 80% power at the 0.05 level and will thus require 16 subjects for each of two arms.

Treatment Assignment Procedures

Subjects will be randomized to treatment A or B in a blinded fashion using the randomization algorithm within REDCap. The randomization module in REDCap implements a defined randomization model within the project, allowing the site to randomize the subjects. In this module, randomization model is defined as Drug A and Drug B in a 1:1 ratio. Drug A and Drug B may refer to placebo or active drug, however they are left coded as such to ensure blinding. The module creates a template allocation table, which the user uses to structure the randomization table to be imported. The module also monitors the overall allocation progress and assignment of randomized subjects to ensure balanced proportions of active drug and placebo. Only one site member will be allowed randomization privileges, but the site will confirm, and lock the specific data field to ensure that no data is altered after randomization. There is no stratification, and there are no variable block sizes.

Trial randomization codes for each individual subject will be retained within the REDCap data set as treatment A or B. The independent statistician retains the identity of A or B and does not disclose this to the study conductors. The planned breaking of the code will occur after data analysis is complete. Unplanned breaking of the code will occur if a medical condition mandates such an action.

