9.5 Outcomes

Outcomes will be analyzed when all patients have completed the study at day 56 by both PIs and the statistical consultant on this study ([name]) who will be blinded from the study group until the data analysis is completed.

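### The blind is fragile: one two-letter code covers all 36 participants, and the statement that no collected data can identify the arm is wrong while ginger metabolites are assayed

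*Combined protocol and SAP*

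**What the plan says.** There is one treatment code per arm. Section 5.2: "Each bottle is labeled 'A' or 'B' and the code is held by the research pharmacy". Section 3: "In this module, randomization model is defined as Drug A and Drug B in a 1:1 ratio". The coordinator retrieves the allocation from REDCap (sections 3, 4.3 and 6.2.2), then collects the lettered bottle from the pharmacy and gives it to the participant (5.2). Section 9.2 adds: "Trial randomization codes for each individual subject will be retained within the REDCap data set as treatment A or B".

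The PIs may break the blind for a safety concern, a serious adverse event or a DSMB concern (6.2.3, 9.2). No procedure limits that disclosure to one participant.

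Section 6.2 provides for assay of 6-shogaol and 6-gingerol metabolites in 8 participants at Visits 3, 4 and 5. The Précis closes recruitment to this subset by letter: "Once there have been 4 subjects in Group A and 4 subjects in Group B selected". Sections 3, 6.2 and 6.2.4 define it instead as 4 males and 4 females.

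On what the data can reveal, section 6.2.3 says, and 9.2 repeats: "All study data is collected objectively without an opportunity for the collected data to identify the study arm". Section 9.5 has both PIs and the statistical consultant analyse the outcomes, and describes the analysis as done by people "who will be blinded from the study group until the data analysis is completed". Section 9.2 says: "The planned breaking of the code will occur after data analysis is complete".

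**The concern.** A code with two values for the whole trial cannot be broken for one person. Telling an investigator what one participant received also tells them what the letter means, and so what everyone received or will receive. The protocol itself creates two ways to learn this: emergency unblinding, and an assay of compounds that mark ginger intake. It provides no safeguard for the second, because it says that no such data exist.

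Spirometry and the methacholine challenge depend on patient effort and on the operator. PD20 is a primary outcome and FEV1 a secondary one. The PIs and coordinator collect the data (10.1) and review case report forms monthly (10.3.2), and the PIs take part in the analysis. With 18 per arm, modest differences in coaching or data handling could matter.

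**Working it through.** **1. Number randomised (section 9.2).** 16 per arm with 10% attrition: 16 / (1 − 0.10) = 17.8, rounded up to 18 per arm; 2 × 18 = 36. The plan's figure reproduces.

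**2. Allocations exposed by one code break.** Each letter is shared by 18 participants. Identifying one letter identifies its 18 holders and, by elimination, the other 18: 18 + 18 = 36 of 36. With a unique code per participant it is 1 of 36. This counts allocations that become known to someone who sees the letters. It does not count measurements biased.

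**3. How often this could happen.** The documents give no unblinding rate, so the rates below are assumptions. If each participant independently has probability p of an individual code break:

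| Assumed p | Chance of at least one break, 1 − (1 − p)^36 | Expected allocations exposed, shared code (36 × that chance) | Expected allocations exposed, unique codes (36p) |
|---|---|---|---|
| 1% | 30% | 10.9 | 0.36 |
| 2% | 52% | 18.6 | 0.72 |
| 5% | 84% | 30.3 | 1.8 |

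**4. Size of the PK route.** Section 6.2 gives 8 participants, 3 visits and 7 time points: 8 × 3 × 7 = 168 samples. If 4 are on ginger, 4 × 3 × 7 = 84 samples come from them, of which 4 × 3 × 6 = 72 are post-dose. If the subset is instead 4 males and 4 females, the number on ginger is not fixed. Treating the 8 as a random draw from 18 + 18, the chance that none is on ginger is C(18,8) / C(36,8) = 0.0014. The data can therefore identify a letter under either definition.

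**5. The blinding statement against the assay.** Sections 6.2.3 and 9.2 support the statement with PD20 and FeNO, whose changes occur in both arms. Neither considers the metabolite data in section 6.2. Serial pre-dose to 8-hour profiles of ginger metabolites can identify who takes ginger, so the statement is incorrect. No section delays PK results until after the analysis. Section 10.2 labels samples with a study number, but the key is held by three people who, read with 10.1, appear to be the coordinator and the two PIs.

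**6. Who holds the code.**

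| Place | Code holder |
|---|---|
| 5.2 | Research pharmacy |
| 6.2.3 | Independent statistician; pharmacy does not know which letter is ginger |
| 9.2, treatment assignment | Independent statistician |
| 9.2, emergency unblinding | Research pharmacy |

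The two emergency routes name different contacts, and section 9.2 disagrees with itself.

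**The case against.** The strongest reply is that the plan defines its blind as A/B coding with the identity withheld, and that seeing a letter reveals no treatment. That stands. A reader might infer that lettered bottles contradict the double blind; they do not. The scheme holds until a letter is identified, and the only direct contradiction is with the statement about collected data.

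A reader might also infer that one code break makes every later measurement open-label. The documents do not support this. A break goes to the PIs, and nothing says that participants are told. Capsules match in appearance and taste (5.2), so other participants stay blind. The ACT is self-administered (section 7), and eosinophils and cytokines are laboratory assays. Measurements already completed cannot be affected.

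The PK route is conditional. Samples are coded and shipped to another laboratory, and a result must come back and be linked to a letter before it decodes anything. The documents neither say that results return early nor forbid it. If they arrive after the last visit, only the analysis is exposed. A reader might infer that a single plasma value suffices. That is unsupported: only ginger supplements are excluded (4.2), not dietary ginger, and no concentrations are given. A full profile should be much harder to misread, but that is inference.

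Emergency unblinding may also be rare: section 2.2 reports no adverse event above Grade 1 in earlier 28-day studies. This bears on likelihood. It does not supply the missing safeguard or make the blinding statement correct.

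**Conclusion.** The point holds as a weakness of the blinding scheme plus one incorrect statement. Identifying one letter exposes 36 of 36 allocations to site staff who see the letters, against 1 of 36 with subject-specific codes. That count rests only on the documents. The probabilities in step 3 rest on assumed rates and are illustrative.

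The statement in 6.2.3 and 9.2 is wrong as written. Whether the PK data would actually unblind anyone depends on results being returned and linked to letters before analysis, which the plan leaves open. Code custody and the PK subset definition are contradictory in the text and must be reconciled. None of this shows that the blind has been broken. The plan should be changed because the protection is cheap and one primary outcome depends on the operator.

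**What to change.** 1. Over-label bottles with subject-specific kit numbers linked to the REDCap allocation, covering the letter. Show the coordinator the kit number only and keep the A/B field out of site view, so that one code can be broken alone.
2. Have the PK laboratory hold metabolite results under separate sample IDs, with the key kept by the independent statistician, and release them only after database lock and completion of the primary analysis. Do this even if relabelling is declined.
3. Correct the statement in 6.2.3 and 9.2: name the metabolite data as able to identify the arm and refer to the embargo.
4. Reconcile 5.2, 6.2.3 and 9.2 so that one code holder and one emergency contact are named. Reconcile the PK subset definition in the Précis with sections 3, 6.2 and 6.2.4. Any count by group should be done by the independent statistician.

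Cost: step 1 needs modest pharmacy relabelling, and step 2 needs a second sample key and a laboratory release procedure. Steps 3 and 4 are changes of text, apart from moving any by-group count to the independent statistician. The intervention, sample size and power stay as they are.
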